10.1.7. Data quality assurance

The investigator should maintain a record of the location(s) of their respective essential documents including source documents. The storage system used during the trial and for archiving (irrespective of the type of media used) should provide for document identification, version history, search, and retrieval.

Essential trial documents may be added or removed where justified (in advance of trial initiation) based on their importance and relevance to the trial. When a copy is used to replace an original document (e.g. source documents, CRF), the copy should fulfil the requirements for certified copies.

CONFIDENTIAL209544 (RSV MAT-004)
Protocol Amendment 3 Final

All subject data relating to the study will be recorded on printed or electronic CRF unless transmitted to the sponsor or designee electronically (e.g. laboratory data). The investigator is responsible for verifying that data entries are accurate and correct by physically or electronically signing the eCRF.

The investigator must maintain adequate and accurate source documents and trial records that include all pertinent observations on each of the site's trial subjects (see [Glossary of terms](#) for the exact definition of source documents) that supports information entered in the eCRF.

The investigator must permit study-related monitoring, audits, IRB/IEC review, and regulatory agency inspections and provide direct access to source documents or certified copies.

The sponsor or designee is responsible for the data management of this study including quality checking of the source data.

Study monitors will perform ongoing source data verification to confirm that data entered into the eCRF by authorised site personnel are attributable, legible, contemporaneous, original, accurate, and complete. Changes to source data should be traceable, should not obscure the original entry, and should be explained if necessary (e.g. via an audit trail). The safety and rights of subjects must be protected and study be conducted in accordance with the currently approved protocol and any other study agreements, ICH GCP, and all applicable regulatory requirements.

Trial records and source documents, including signed ICF, pertaining to the conduct of this study must be retained by the investigator for 25 years from the issue of the final Clinical Study Report (CSR)/equivalent summary unless local regulations or institutional policies require a longer retention period. No records may be destroyed during the retention period without the written approval of the sponsor. No records may be transferred to another location or party without written notification to the sponsor.

10.1.8. Source documents

Source documents provide evidence for the existence of the subject and substantiate the integrity of the data collected. Investigator should maintain a record of the location(s) of their source documents.

Data entered in the eCRF that are transcribed from source documents must be consistent with the source documents or the discrepancies must be explained. The investigator may need to request previous medical records or transfer records, depending on the study. Also, current medical records must be available.

Definition of what constitutes source data and source documents can be found in the [Glossary of terms](#).

CONFIDENTIAL209544 (RSV MAT-004)
Protocol Amendment 3 Final**10.1.9. Study and site start and closure**

GSK or its designee reserves the right to close the study site or terminate the study at any time for any reason at the sole discretion of GSK, provided there is sufficient notice given to account for patient's safe exit from study participation. Study sites regular closure will occur upon study completion. A study site is considered closed when all required data/documents and study supplies have been collected and a study-site closure visit has been performed.

The investigator may initiate study-site closure at any time, provided there is reasonable cause and sufficient notice is given in advance of the intended termination.

Reasons for the early closure of a study site by the sponsor or investigator may include but are not limited to:

- Failure of the investigator to comply with the protocol, the requirements of the IRB/IEC or local health authorities, the sponsor's procedures, or GCP guidelines
- Inadequate recruitment of subjects by the investigator
- Discontinuation of further study intervention development

10.1.10. Publication policy

GSK aims to submit for publication the results of these studies in searchable, peer reviewed scientific literature within 18 months from Last Subject Last Visit (LSLV) for interventional studies and follows the guidance from the International Committee of Medical Journal Editors.

10.2. Appendix 2: Clinical laboratory tests

Study-required laboratory assessments detailed in [Table 26](#), except urinalysis, should be performed by a central laboratory. During special circumstances, hematocrit may be performed locally if it is not possible to collect a blood sample for central analysis using GSK-provided supplies (see [Section 8](#)).

CONFIDENTIAL209544 (RSV MAT-004)
Protocol Amendment 3 Final**Table 26 Protocol-Required Safety Laboratory Assessments**

| Laboratory Assessments | Parameters |
|------------------------|---|
| Hematology | Leukocytes (White Blood Cells) |
| | Lymphocytes |
| | Neutrophils |
| | Eosinophils |
| | Platelets |
| | Erythrocytes (Red Blood Cells) |
| | Hematocrit |
| | Hemoglobin |
| | Erythrocyte Mean Corpuscular Volume (MCV) |
| | Aspartate Aminotransferase (AST) / Serum Glutamic-Oxaloacetic Transaminase (SGOT) |
| | Alanine Aminotransferase (ALT) / Serum Glutamic-Pyruvic Transaminase (SGPT) |
| | Creatinine |
| | Urea nitrogen |
| | Urinalysis by dipstick |
| Protein | |

Assessment of eligibility and grading of laboratory parameters will be based on reference ranges described in [Sheffield, 2013] and the SPM for this study.

10.3. Appendix 3: Adverse Events: definitions and procedures for recording, evaluating, follow-up, and reporting

10.3.1. Definition of an Adverse Event (AE)

An AE is any untoward medical occurrence in a patient or clinical study subject, temporally associated with the use of a study intervention, whether or not considered related to the study intervention.

NOTE: An AE can therefore be any unfavourable and unintended sign (including an abnormal laboratory finding), symptom, or disease (new or exacerbated) temporally associated with the use of a study intervention.

| Events Meeting the AE Definition |
|--|
| 
 • Significant or unexpected worsening or exacerbation of the condition/indication under study. • Exacerbation of a chronic or intermittent pre-existing condition including either an increase in frequency and/or intensity of the condition. • New conditions detected or diagnosed after study vaccine(s)/product(s) administration even though they may have been present prior to the start of the study. • Signs, symptoms, or the clinical sequelae of a suspected interaction. • Signs, symptoms, or the clinical sequelae of a suspected overdose of either study vaccine(s)/product(s) or a concurrent medication (overdose per se should not be reported as an AE/SAE). |

CONFIDENTIAL209544 (RSV MAT-004)
Protocol Amendment 3 Final

- Signs or symptoms temporally associated with study vaccine(s)/product(s) administration.
- Signs, symptoms that require medical attention (e.g. hospital stays, physician visits and emergency room visits)
- Pre- or post- intervention events that occur as a result of protocol-mandated procedures (i.e. invasive procedures, modification of participant's previous therapeutic regimen).
- Clinically significant abnormal laboratory findings or other abnormal assessments that are present at baseline and significantly worsen following the start of the study will also be reported as AEs or SAEs.
- AEs to be recorded as solicited AEs are described in the Section [10.3.3](#). All other AEs will be recorded as UNSOLICITED AEs.

Events NOT Meeting the AE Definition

- Situations where an untoward medical occurrence did not occur (e.g. social and/or convenience admission to a hospital, admission for routine examination).
- Anticipated day-to-day fluctuations of pre-existing disease(s) or condition(s) present or detected at the start of the study that do not worsen.
- Pre-existing conditions or signs and/or symptoms present in a participant prior to the study vaccination. These events will be recorded in the medical history Section of the eCRF.
- Hospitalisation for elective treatment of a pre-existing condition (known or diagnosed prior to informed consent signature) that did not worsen from baseline.
- Clinically significant abnormal laboratory findings or other abnormal assessments that are associated with the disease being studied, unless judged by the investigator as more severe than expected for the participant's condition, or that are present or detected at the start of the study and do not worsen.
- Disease-related events (DRE), typically associated with the disease under study. These events will be recorded in the participant's eCRF and will be monitored by the IDMC on a routine basis.

However, if 1 or both of the following conditions apply, then the event should be reported promptly to GSK as an SAE (see Section [10.3.8](#)):

- The event is, in the investigator's opinion, of greater intensity, frequency, or duration than expected for the individual subject, or
- The investigator considers that there is a reasonable possibility that the event was related to the administration of the study vaccine/product

CONFIDENTIAL209544 (RSV MAT-004)
Protocol Amendment 3 Final**10.3.2. Definition of a Serious Adverse Event (SAE)**

| | |
|--|---|
| An SAE is any untoward medical occurrence that: | |
| a. | Results in death |
| b. | Is life-threatening Note: The term ‘life-threatening’ in the definition of ‘serious’ refers to an event in which the participant was at risk of death at the time of the event. It does not refer to an event, which hypothetically might have caused death, had it been more severe. |
| c. | Requires hospitalisation or prolongation of existing hospitalisation Note: In general, hospitalisation signifies that the participant has been admitted at the hospital or emergency ward for observation and/or treatment that would not have been appropriate in the physician’s office or in an out-patient setting. Complications that occur during hospitalisation are also considered as AEs. If a complication prolongs hospitalisation or fulfils any other serious criteria, the event will also be considered serious. When in doubt as to whether ‘hospitalisation’ occurred, or was necessary, the AE should be considered serious. |
| d. | Results in disability/incapacity Note: The term disability means a substantial disruption of a person’s ability to conduct normal life functions. This definition is not intended to include experiences of relatively minor medical significance such as uncomplicated headache, nausea, vomiting, diarrhoea, influenza like illness, and accidental trauma (e.g. sprained ankle) which may interfere or prevent everyday life functions but do not constitute a substantial disruption. |
| e. | Is a congenital anomaly/birth defect in the offspring of a study participant |
| f. | Abnormal pregnancy outcomes (e.g. spontaneous abortion, foetal death, stillbirth, congenital anomalies, ectopic pregnancy). |
| g. | Other situations Medical or scientific judgement should be exercised in deciding whether reporting is appropriate in other situations, such as important medical events that may not be immediately life-threatening or result in death or hospitalisation but may jeopardise the participant or may require medical or surgical intervention to prevent one of the other outcomes listed in the above definition. These should also be considered serious. Examples of such events are invasive or malignant cancers, intensive treatment in an emergency room or at home for allergic bronchospasm, blood dyscrasias or convulsions that do not result in hospitalisation. |

CONFIDENTIAL209544 (RSV MAT-004)
Protocol Amendment 3 Final**10.3.3. Solicited events****a. Solicited administration site events**

The following administration site events will be solicited:

Table 27 Solicited administration site events

| All age groups |
|----------------|
| Pain |
| Redness |
| Swelling |

b. Solicited systemic events

The following systemic events will be solicited:

Table 28 Solicited systemic events

| Adult/Child (≥ 6 years) |
|-------------------------------|
| Fatigue |
| Fever |
| Nausea |
| Vomiting |
| Diarrhea |
| Abdominal pain |
| Headache |

Note: maternal subjects will be instructed to measure and record the (preferably) oral temperature at least once each day, at approximately the same time each day. Should additional temperature measurements be performed at other times of day, subjects will be instructed to record the highest temperature in the electronic Subject Diary (e-Diary).

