| | SAEs related to study participation or concurrent GSK medication or vaccine | | M | | | | | | | | | | |

* Approximately monthly contacts pre- and post-delivery also occur within the timeframes described above and are described in Section 1.3. **i.e. consent obtained. Pre = pre-vaccination; V=visit; C = contact; D= Day. *** if subsequent pregnancy occurs during the study, follow-up extends up to 8 weeks post birth of the infant If subsequent pregnancy occurs after Visit 8, report adverse pregnancy outcomes / other SAEs experienced by mother / infant, if known. ****AESIs include adverse pregnancy outcomes, pregnancy related AEs of special interest and neonatal AEs of special interest. Neonatal AEs of special interest identified after V2-NB (e.g., congenital anomalies) will continue to be reported as such

CONFIDENTIAL209544 (RSV MAT-004)
Protocol Amendment 3 Final

The investigator or designee will record and immediately report all SAEs (including RTIs associated with hospitalization of a maternal or infant subject and all adverse pregnancy outcomes), as well as all pregnancy related AESIs and neonatal AESIs to the sponsor or designee via the Expedited AE Reporting Form. This reporting should under no circumstances occur later than 24 hours after the investigator becomes aware of the event, as indicated in Section 10.3.10. The investigator will submit any updated data to the sponsor within 24 hours of it being available.

A post-study AE/SAE is defined as any event that occurs outside of the AE/SAE reporting periods defined in Table 21. Investigators are not obligated to actively seek AEs or SAEs in former study subjects. However, if the investigator learns of any SAE, including a death, at any time after a subject has been discharged from the study, and he/she considers the event to be reasonably related to the study vaccine(s)/product(s), the investigator will promptly notify the Study Contact for Reporting SAEs mentioned in Table 23.

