8.3.3. Regulatory reporting requirements for SAEs, subsequent pregnancies, and other events

Once an investigator (or designee) becomes aware that a study subject has experienced an SAE/AESI/subsequent pregnancy, he/she must report it to GSK using the documentation and within the timeframes mentioned in Table 22. This is essential for meeting legal obligations and ethical responsibilities for the subject safety and the safety of a study intervention under clinical investigation.

For SAEs/AESIs, the investigator will always provide an assessment of causality at the time of the initial report as defined in Section 10.3.9.2.

Local regulatory requirements and sponsor policy for the preparation of an investigator safety report for Suspected Unexpected Serious Adverse Reactions (SUSAR) must be followed. These reports will be forwarded to investigators as necessary.

The sponsor has a legal responsibility to notify local authorities and other regulatory agencies about the safety of a study intervention under clinical investigation. The sponsor will comply with country-specific regulatory requirements related to safety reporting to the regulatory authority, IRB/ IEC, and investigators.

Please refer to Section 10.3.10 for further details regarding the reporting of SAEs/AESIs/subsequent pregnancies

Table 22 Timeframes for submitting serious adverse event, subsequent pregnancy and other event reports to GSK

| Type of Event | Initial Reports | | Follow-up of Relevant Information on a Previous Report | |
|---|-----------------|--|--|--|
| | Timeframe | Documents | Timeframe | Documents |
| SAEs (including adverse protocol pregnancy outcomes) | 24 hours* ‡ | electronic Expedited Adverse Events Report | 24 hours* | electronic Expedited Adverse Events Report |
| AESIs | 24 hours** ‡ | electronic Expedited Adverse Events Report | 24 hours* | electronic Expedited Adverse Events Report |
| Maternal subjects: MA-RTIs Infant subjects: RTIs/LRTIs | 3 days* | eCRF | 1 week | eCRF |
| Subsequent Pregnancies | 2 weeks* | electronic pregnancy report | 2 weeks* | electronic pregnancy report |

* Timeframe allowed after receipt or awareness of the information by the investigator/site staff.

**Timeframe allowed once investigator determines event meets protocol definition of an AESI.

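### Section 10.3.1 exempts undefined disease-related events from AE status, which conflicts with the Section 8.3.1 rule that every hospitalised RTI is an SAE and leaves RSV illness open to inconsistent SAE and MAE classification

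*Protocol*

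**What the plan says.** In the Protocol, Section 10.3.1, the list of events that do not meet the AE definition includes "Disease-related events (DRE), typically associated with the disease under study". On what becomes of them, the clause says: "These events will be recorded in the participant's eCRF and will be monitored by the IDMC on a routine basis". Such an event is then to be sent to the sponsor as an SAE if at least one of two conditions applies. The first compares the case with its usual course: "The event is, in the investigator's opinion, of greater intensity, frequency, or duration than expected for the individual subject". The second condition concerns causality, and is met when the investigator thinks the vaccine may reasonably have played a part. No list or definition of disease-related events is given.

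Section 8.3.1 obliges the investigator to "report all SAEs (including RTIs associated with hospitalization of a maternal or infant subject and all adverse pregnancy outcomes". The limit is 24 hours from awareness, and no test of severity or causality is applied.

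Section 8.3.3, Table 22, gives SAEs 24 hours by expedited report. A separate row, "Maternal subjects: MA-RTIs Infant subjects: RTIs/LRTIs", allows three days and uses the eCRF.

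**The concern.** The vaccine is meant to prevent RSV lower respiratory illness in infants (Section 2.1), so the disease under study is most naturally read as RSV illness. On that reading, an infant admitted with RSV illness that the investigator regards as ordinary and unrelated is not an AE under Section 10.3.1 and is an SAE under Section 8.3.1. A site can defend either course from the text.

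Infant SAEs and MAEs are a primary safety endpoint to 6 weeks and secondary endpoints to 6 months and 1 year (Table 5); maternal SAEs and MAEs are primary to 6 weeks and secondary to 6 months after delivery. If classification turns on one investigator's view of one case, those counts partly reflect site practice. A modest excess of RSV illness may show only as a difference between groups, and it cannot show in AE tables from which the ordinary-looking cases were withheld.

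**Working it through.** The protocol states no figure for this point, so the main check sets the passages side by side. One stated power figure bears on how far the consequence reaches, and it is reproduced in step 4.

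1. **Hospitalised RTI, judged as expected and unrelated.** Section 10.3.1, disease-related clause: not an AE. Section 8.3.1: SAE, 24 hours. Section 10.3.2 c: hospitalisation makes an untoward occurrence serious. The passages disagree.

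2. **Medically attended RTI without admission.** The same Section 10.3.1, under events that do meet the AE definition, counts symptoms that need medical attention, physician visits included. The disease-related clause says the opposite if the illness is RSV. For mothers, Section 10.3.8 places medically attended RTIs among the medically attended AEs, and Table 1 has a row for the (S)AEs that correspond to them. For infants, Section 10.3.8 names RTIs separately, so it does not settle the matter.

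3. **The two conditions.** The first needs an expected course for that subject. Mothers must be healthy at entry (Section 5.1.1) and infants enter at birth (Section 5.1.2), so no existing disease supplies one. The second sends an event straight from non-AE to SAE, even a mild one, if it is judged possibly related.

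4. **Does the enhanced-disease assessment depend on AE coding?** Section 8.2.3.4 claims at least 90% power with 5 infant infections to show a progression rate below 80% when the true rate is 10%, one-sided 5%. With X the number progressing:
   - P(X ≤ 1 | 0.80) = 0.2⁵ + 5 × 0.8 × 0.2⁴ = 0.00032 + 0.00640 = 0.0067.
   - P(X ≤ 2 | 0.80) = 0.0579, above 0.05, so the rule is X ≤ 1.
   - Power = P(X ≤ 1 | 0.10) = 0.9⁵ + 5 × 0.1 × 0.9⁴ = 0.5905 + 0.3281 = 0.919.

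   The stated power reproduces. Its inputs are confirmed infections and how many progressed to severe disease or hospitalisation. No SAE or MAE code enters.

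5. **Birth to 6 months.** RTI surveillance (Section 8.4.2), case definitions applied at analysis (Section 4.2.6), by-group tables of RSV-LRTI, its severe forms and RSV hospitalisation (Section 9.4.4.1), and IDMC reports that list RTI/LRTI separately from SAEs (Section 8.2.3.3.3) all work whatever the AE code.

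6. **From 6 to 12 months.** Infant RTI surveillance ends at Visit 4-NB (Section 8.4.2), and the RSV endpoints stop at 6 months (Section 9.4.4.1). The remaining pre-specified infant safety endpoints are SAEs, MAEs and AEs leading to withdrawal (Table 5). An RSV admission at 8 months handled as a disease-related event therefore enters no pre-specified endpoint. Table 6 labels this epoch single-blind, which the glossary defines as investigator and/or staff aware of assignment. Section 4.2.5 adds that the study is not considered observer-blind after the second analysis. The judgement may thus be made by someone who knows the arm, so misclassification could differ between groups.

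7. **Holding rules (Table 17).** In rule 1a, maternal death, fetal death and unexplained infant death stand without SAE coding; only the life-threatening-SAE limb depends on it.

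**The case against.** The strongest reply is that the specific text already wins. No passage says an RTI is a disease-related event, and the clause looks like template wording. Section 8.3.1 names hospitalised RTIs as SAEs outright, so a site would have to prefer a general, undefined bullet to an explicit rule. The absence of an expected course can also be read as leaving the clause little to act on. Cases worse than expected, which is how enhanced disease would present, return to SAE reporting; the clause keeps the rest under IDMC monitoring; and the IDMC may recommend a hold outside the rules (Section 8.2.3.3.2). Neonatal respiratory infection and distress are also AESIs, with a 24-hour clock once the definition is met.

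Most of this stands, and it rules out three stronger readings that a reader might infer:

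- **That the clause removes the enhanced-disease signal.** It does not. Section 8.3.1 still makes these admissions SAEs, and the channels in steps 4 and 5 follow the risk to 6 months without AE codes.
- **That it disables holding rule 1b.** Rule 1b needs an SAE with no reasonable cause other than vaccination. A case judged unrelated would not normally meet it even if coded as an SAE, and a case judged possibly related returns through the second condition.
- **That 10% to 40% of RSV cases are at stake**, from 1 of 10 to 2 of 5 using the denominators in Table 20. Those rows are illustrations, not forecasts, and such infants would still count towards the RSV-hospitalisation endpoint to 6 months.

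What does not stand is the claim that nothing needs changing. The protocol states no order of precedence between the two sections, and steps 2 and 6 are not answered by Section 8.3.1 for non-admitted infants.

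**Conclusion.** The contradiction is real. Its consequence is inconsistent, judgement-dependent classification of RSV respiratory illness in the SAE and MAE tables and in one limb of holding rule 1a. The exposure is greatest for infants from 6 to 12 months, where no parallel RSV endpoint remains and the arm may be known.

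The size cannot be given as a number: the protocol states neither how many RTI admissions or attended RTIs to expect nor how many sites would follow the clause. Per case, the difference is SAE or not, MAE or not, and, during RTI surveillance, a 24-hour expedited report or only the 3-day eCRF entry.

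The conclusion assumes that the disease under study means RSV illness. If the sponsor meant something else, the text does not say so, and it still needs clarification.

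**What to change.** Reconcile the passages so that one rule governs. Either delete the disease-related-event bullet and its two conditions from Section 10.3.1, or add a sentence that the bullet does not apply to respiratory tract illness in mothers or infants. The rule already in Section 8.3.1 then governs hospitalised RTIs, and the general AE statement in Section 10.3.1 covers attended RTIs without admission. The RTI eCRF page stays as an additional record.

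The cost is one edited paragraph and a short clarification to sites, with no new procedure. The downside is a few more expedited reports of ordinary RSV admissions.
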